#### 6 DATA COLLECTION

# **6.1 Summary of Data Management**

Data collection will occur at three stages: 1) primary data collection by the study team during the index ED visit; 2) follow-up data collection at 1-, 7- and 30-days post-ED visit; 3) secondary data collection using EHR query and, if needed, manual chart review. All data will be centrally stored in REDCap. Access to the study REDCap database will be made available only to study team members.

# 6.2 Primary data collection during index ED visit

A study team member (coordinator or other investigator) other than the proceduralist performing the ESPB will assess pain prior to and 1 hour after the procedure. Prior history of kidney stones and urologic procedures will be collected. A safety screen will also be performed prior to procedure by the proceduralist. Data entry into REDCap will occur via electronic case reporting form.

# 6.3 Follow up assessments via web-based survey

At day 1, 7 and 30 after the ED visit, a brief web-based survey will be administered to the participant via E-mail with or without telephone assistance based on the participant's preference. This survey form will assess pain management after the index ED visit, return visits to the ED, and other outpatient follow up or interventions for kidney stones. Each follow up assessment will also evaluate for known complications of ESPB and other adverse events. All follow up assessments are part of the optional sub-study optional except for the assessment of adverse events at day 30.

# 6.4 Secondary data collection from the EHR

Variables regarding patient demographics, ED operations metrics, diagnoses, medical history, procedures performed, other healthcare encounters, nurse assessments of pain, medications administered, and prescriptions provided during the index ED visit will be obtained using direct query to the EHR databases (RDW, HSDW, Caboodle, Clarity) and confirmed with manual chart review if needed. Using the same EHR query we will also collect data regarding historical control patients (external controls that did not receive ESPB). Control patient data will be collected as secondary data collection of routinely collected health information.

# 6.5 Data storage

All data used in this study will be centrally stored in REDCap. This study is anticipated to take up to 2 years to complete. The REDCap database will be placed into archive mode and stored for 7 years after this point for recordkeeping purposes.

#### 7 DATA ANALYSIS PLAN

# 7.1 Descriptive analysis and statistical testing

The primary exposure of interest is performance of ESPB for uncomplicated renal colic in the ED. We will describe the center and spread for all collected variables. Additionally, we will compare data from participants to historical control patients whose data is collected secondarily from query to the EHR. Continuous variables will be described by medians with interquartile ranges and differences will be assessed by two-sample t-test or Wilcoxon's rank sum test depending on distribution. Categorical variables will be described by counts with proportions and differences assessed using the Chi-squared test or Fisher's exact test where appropriate. An alpha = 0.05 will be considered the level of significance in all analyses.

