#### 3.6.2 Secondary Outcomes

- Difference in visual analog scale pain (1-10) from prior to procedure to first pain assessment after 60 minutes from completion of ESPB assessed by bedside nurse
  - Historic data from the U-M ED suggests that the median maximal pain reduction (last pain score minus first) in the ED is a mean reduction of 3.4 points (SD = 3.0) from a starting value of 7.9.
- ED operational quality metrics:
  - o Rate of admission to hospital
  - Rate of 72-hour return to the ED
  - ED length of stay
- Safety outcomes and complications at day 30

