# 4.4 Selection of external control patients

External control patients will be selected from a population of patients meeting the following criteria: 1) adult ED patient with the diagnosis of uncomplicated kidney stones; 2) received at least one dose of parenteral medication while in the ED; 3) presentation to the ED between 7/1/2021 and the study start date. From this population, propensity score matched control patients will be selected at a ratio of 3 controls to 1 ESPB patient. External control population patients are not active patients in this study and analysis of their data will be secondary use of data collected during routine care. To provide valid comparison between control patients and ESPB patients, we will compare pain scores obtained by the treatment team (bedside nurse). For all other primary and secondary outcomes, data collection utilizes EHR query that does not require prospective data collection. Please see the data collection section of this protocol for further details.

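### If bedside-nurse pain scores are compared with external controls, the only two-group test named ignores starting pain, and sections 4.4 and 7.4 disagree on whether that comparison is made

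*Combined protocol and SAP*

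**What the plan says.** The first secondary outcome in section 3.6.2 is a change score measured by the bedside nurse: "Difference in visual analog scale pain (1-10) from prior to procedure to first pain assessment after 60 minutes from completion of ESPB". As background, the same section reports that the historical change in the department "is a mean reduction of 3.4 points (SD = 3.0) from a starting value of 7.9". That figure is for the last score minus the first, not for the hour around a procedure.

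Section 4.4 states the comparison with controls: "To provide valid comparison between control patients and ESPB patients, we will compare pain scores obtained by the treatment team (bedside nurse"). Section 7.1 supplies the method for continuous variables: "Continuous variables will be described by medians with interquartile ranges and differences will be assessed by two-sample t-test", or by a rank-sum test, depending on distribution. No section names a covariate, a regression model or an allowance for matched sets in the pain analysis. Section 7.2 does put the first nurse pain score of the visit into the propensity model.

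Section 7.4 points the other way from section 4.4. It groups change in pain score with complications, satisfaction and survey results as things only block recipients have, to be analysed within patient or descriptively. Its bracketed list of EHR outcomes to be compared with controls names operations metrics and opioid use, but not pain. It excludes comparison with controls only for data collected prospectively, such as pain scores taken by investigators.

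**The concern.** The comparison is not randomised. A two-sample test of raw change leaves two things on the table.

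- **Precision.** A raw change score fixes the slope of the later score on the earlier one at 1. If the true slope differs, the change score carries variance that a regression on the earlier score would remove.
- **Residual imbalance.** If one group starts higher and the slope is below 1, that group is expected to fall further even with no treatment effect. Matching on the first ED score reduces this but need not remove it. The endpoint starts from the pre-procedure score, and under section 4.2 block patients have already had a parenteral dose before enrolment. The matched score and the starting score can therefore be different measurements.

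At stake is the size and precision of the pain result, which readers will set beside the primary outcome. The endpoint is also anchored on the block, and section 6.4 describes the controls as patients who did not have it. They have no pre-procedure score and no 60-minute score until an index time is assigned.

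**Working it through.** **The plan's own figure.** No sample size or power is stated for pain. The frequentist size stated in section 2.10 is for the binary primary outcome. Simon's optimal design with rates 55% and 75%, alpha 0.05 and beta 0.10 reproduces exactly: continue if more than 10 of 18 respond, succeed if more than 35 of 54 respond, attained alpha 0.0477, power 0.9007. This does not bear on the pain analysis.

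**Inputs.**
- 60 block patients and up to 180 controls (section 2.10).
- SD of change 3.0 (section 3.6.2), used as a proxy because it is for last minus first ED score.
- Alpha 0.05 (section 7.1), taken as two-sided because no sidedness is stated for pain.
- Correlation ρ between earlier and later score: not in the documents, assumed 0.3 to 0.7.
- The two groups are treated as independent samples.

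**Unadjusted change.** SE = 3.0 × √(1/60 + 1/180) = 0.447. Detectable difference at 80% power = (1.960 + 0.842) × 0.447 = 1.25 points. Power for a 1-point difference is 60.9%.

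**Adjusted, equal SDs s before and after.** Var(change) = 2s²(1 − ρ). Residual variance after regression on the earlier score = s²(1 − ρ²). The ratio is (1 + ρ)/2, so the adjusted SD = 3.0 × √((1 + ρ)/2). The slope is ρ, so each point of starting imbalance shifts the raw change contrast by 1 − ρ.

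| ρ | Variance ratio | Adjusted SD | Detectable difference | Power for 1 point | Shift per point of imbalance |
|---|---|---|---|---|---|
| 0.3 | 0.65 | 2.42 | 1.01 | 79.2% | 0.7 |
| 0.5 | 0.75 | 2.60 | 1.09 | 73.3% | 0.5 |
| 0.7 | 0.85 | 2.77 | 1.16 | 67.9% | 0.3 |

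ρ = 0.7 is about the upper edge. A variable on 1 to 10 with mean 7.9 has variance at most (10 − 7.9)(7.9 − 1) = 14.49. Equal SDs give s² = 9/[2(1 − ρ)], so ρ cannot exceed 1 − 9/(2 × 14.49) = 0.69.

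**Adjusted, later SD 1.5 times the earlier SD (assumed).** Var(change) = s²(3.25 − 3ρ), residual variance = 2.25s²(1 − ρ²), slope = 1.5ρ.
- ρ = 0.3: 2.0475/2.35 = 0.87, a saving of about 13%. Detectable difference 1.25 × √0.87 = 1.17. Shift per point 1 − 0.45 = 0.55.
- ρ = 0.5: 1.6875/1.75 = 0.96, a saving of about 4%. Detectable difference 1.25 × √0.96 = 1.23 (unrounded inputs). Shift per point 1 − 0.75 = 0.25.

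The gain therefore depends on the ratio of SDs as well as on ρ. It vanishes when the slope is 1. In no case is the adjusted residual variance larger than that of the raw change.

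**The case against.** Four points can be made against this.

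1. *The test is not clearly planned for this outcome.* The rule in section 7.1 is general, and the section closest to the outcome, 7.4, describes within-patient or descriptive analysis. This stands in part. A reader might infer that the plan has firmly chosen an unadjusted two-sample test of pain change. The documents do not settle that. But section 4.4 does announce a comparison of nurse scores, and section 7.4 rules out comparison only for prospectively collected data, which EHR nurse scores are not. The likelier reading is that nurse scores are compared and investigator scores are not, and the sections still need to be brought into line.

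2. *Starting pain is already handled by matching.* It is partly handled. Bias comes only from imbalance that remains, of unknown size and direction, and only where the slope is not 1. A reader might infer that the change-score result must be biased, but nothing in the documents shows that the matched groups will differ in starting pain.

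3. *Neither method is assured unbiased without randomisation.* This stands. Change scores rely on parallel trends. Regression adjustment relies on no unmeasured confounding given baseline, and is affected by measurement error in the baseline score. Adjustment does not remove confounding by other factors.

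4. *The gain rests on assumptions.* This also stands. ρ is assumed and the SD is a proxy. A start of 7.9 on a 10-point scale makes unequal SDs plausible, and that shrinks the gain. The variance formula does not describe the rank-sum option. Any remaining correlation between group and baseline also takes back some of the precision.

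**Conclusion.** The point holds in conditional form. Sections 4.4 and 7.4 do not agree on whether nurse pain scores are compared with controls. If they are, the only method named is unadjusted, and a baseline-adjusted model is the better choice.

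Under equal SDs and ρ from 0.3 to 0.7, adjustment saves 35% to 15% of the variance and lowers the detectable difference from 1.25 points to between 1.01 and 1.16. With a later SD 1.5 times the earlier one, the saving is about 13% at ρ = 0.3 and 4% at ρ = 0.5. Each point of starting imbalance left after matching would move the raw change contrast by 0.3 to 0.7 point in the first case, and by 0.55 or 0.25 point in the second.

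A reader might also infer that adjusting for the pre-procedure score costs nothing because both scores are already in hand. They are not. Controls have no procedure time, so neither analysis score exists for them until an index time is defined. The planned change-score comparison has the same need, so this is not an extra burden of adjustment. The first ED nurse score is defined in both groups already.

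The outcome is secondary. The primary analysis, the sample size and the futility rule are unaffected.

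**What to change.** 1. Reconcile sections 4.4 and 7.4: state whether bedside-nurse pain scores are compared with controls, and that investigator-collected scores are not.
2. If nurse scores are compared, define an index time for controls, for example anchored on the first parenteral dose. Say which nurse scores count as pre-index and post-index in each group.
3. In sections 7.1 and 7.4, prespecify a linear regression of the post-index nurse score on group, adjusted for the first ED nurse score and, once it is defined, the pre-index nurse score. Cluster the standard errors on matched set. Report the adjusted mean difference with a 95% confidence interval, keep medians and interquartile ranges as description, and state that the estimate remains open to unmeasured confounding.

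The cost is some extra analysis specification, chiefly the index-time rule. No new patient contact is needed: section 6.4 already draws nurse pain assessments and medications given from the EHR for both groups. I assume that these records carry times.

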# 2.10 Sample Size

- This study is a two-stage trial with one planned interim analysis for futility
- Based on the prior 30-month time period (as of May 2022), 572 out of 1071 patients (53.4%) presenting to the ED and meeting the inclusion criteria did not require a 2nd parenteral pain medication during the ED encounter. Thus, we estimate a baseline response rate of 55%.
- Prior work by Nobel et al.¹and Aydin et al.² suggests that no patient will require a second dose of any pain medication after ESPB, but we estimate a conservative response rate of 75% for treatment with ESPB.
- Using Simon's optimal two-stage design with these parameters and  $\alpha$  = 0.05,  $\beta$  = 0.10, we estimate that 18 subjects will be required at the interim analysis and 54 subjects will be required to complete this study.
- Using a Bayesian two-stage design, where interim analysis is planned at one-third total enrollment and a stopping rule if there is only a 10% probability of ESPB demonstrating a 75% response rate, we estimate that 45 total subjects (15 at interim analysis) will be required to achieve a 1.4% chance of stopping early and 95.2% chance of rejecting the null hypothesis.
- This study will aim to achieve a total enrollment of 60 subjects who receive ESPB to account for losses to follow up and withdrawals from the study. Up to 180 (3:1 ratio) historical controls will also be included in the study thus the total enrollment including both treatment and control patients is 240.

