# 7.2 Primary analysis

Our primary analysis will evaluate the proportion of patients receiving ESPB who require a second parenteral pain medication. This outcome will be compared to external control patients who are selected using propensity score matching at a ratio of 3:1. The propensity score model will include the following variables: age, gender, triage acuity level (ESI score), first ED pain score assessed by nursing, Charlson Comorbidity Index, chronic and initial pain medication type. Data for this outcome will be collected via EHR query as above.

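### Section 7.2 names no test for the 3:1 matched primary comparison, so unadjusted independent-sample tests apply by default: usually conservative, weaker than a covariate-adjusted analysis, and open to a shift of a few points if matching is imperfect

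*Combined protocol and SAP*

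**What the plan says.** Section 7.1 says that participants will be compared with historical controls and then lists the tests. For categorical variables: "differences assessed using the Chi-squared test or Fisher's exact test where appropriate". For continuous variables: "differences will be assessed by two-sample t-test or Wilcoxon's rank sum test depending on distribution". It adds: "An alpha = 0.05 will be considered the level of significance in all analyses". Sidedness is not stated.

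Section 7.2 gives the primary comparison: "This outcome will be compared to external control patients who are selected using propensity score matching at a ratio of 3:1". It lists the propensity-model variables (age, gender, triage acuity, first nursing pain score, comorbidity index and pain-medication type). It gives no test, effect measure or confidence interval.

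Section 4.4 repeats the ratio: "propensity score matched control patients will be selected at a ratio of 3 controls to 1 ESPB patient". Section 2.10 sets the ceiling: "Up to 180 (3:1 ratio) historical controls will also be included in the study". No section mentions an analysis that uses the matched sets, adjusts for covariates or weights incomplete sets. None gives a caliper, a replacement rule or a rule for a patient with fewer than three matches.

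Section 7.4 compares the EHR-derived secondary outcomes with the same controls and also names no test.

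**The concern.** Chi-squared, Fisher, two-sample t and rank-sum tests all assume two independent samples. Matching makes the groups more alike on the matching variables than independent samples would be. If those variables predict a second dose, the pooled difference varies less than the test assumes, so the test rejects too rarely under no effect and uses the data inefficiently. First pain score, acuity and initial analgesic plausibly do predict a second dose.

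An unadjusted test also does nothing about imbalance that survives matching. If some ESPB patients get fewer than three controls, plain pooling gives their controls too little weight. At stake are the p-value, power and possibly the estimate for the primary outcome. With no method named, the analyst could also choose one after seeing the data.

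**Working it through.** **1. The plan's own sizing.** Section 2.10 uses Simon's optimal design with response rates of 55% and 75%, α = 0.05 and β = 0.10. An exact binomial search reproduces it: 18 patients at stage 1 (stop at 10 or fewer responses) and 54 in total (reject above 35 responses), with α 0.0477 and power 0.9007. The rule in 7.3 agrees: 8 second doses among 18 leaves 10 responses. This is a one-sample design and does not use the controls.

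**2. Power of the default test.** Inputs: 60 v 180 patients, second-dose rates 25% v 45% (the complements of 75% and 55%), two-sided 0.05 (assumed).
- Pooled rate: (15 + 81)/240 = 0.40.
- SE under no effect: √[0.40 × 0.60 × (1/60 + 1/180)] = 0.0730.
- SE under the alternative: √[0.25 × 0.75/60 + 0.45 × 0.55/180] = 0.0671.
- Power: Φ[(0.20 − 1.96 × 0.0730)/0.0671] = Φ(0.85) ≈ 0.80.

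The sizing used 90%, so the matched comparison has no power to spare.

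**3. Full 1:3 sets with correlated outcomes.** Let ρ be the within-set correlation. The documents give no value, so a range is assumed. The variance of a set's difference is σ²(4/3)(1 − ρ), while the pooled test assumes σ²(4/3). Size is therefore 2[1 − Φ(1.96/√(1 − ρ))]. Simulation at a 45% rate, with power for 45% v 25%:

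| ρ | Size from formula | Size, chi-squared | Size, stratified by set | Power, chi-squared | Power, stratified |
|---|---|---|---|---|---|
| 0 | 0.050 | 0.047 | 0.047 | 0.81 | 0.80 |
| 0.05 | 0.044 | 0.043 | 0.048 | 0.81 | 0.82 |
| 0.10 | 0.039 | 0.039 | 0.049 | 0.82 | 0.84 |
| 0.20 | 0.028 | 0.029 | 0.050 | 0.83 | 0.88 |
| 0.30 | 0.019 | 0.018 | 0.048 | 0.83 | 0.91 |

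With full sets, pooling itself adds no bias.

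**4. Propensity matching simulated directly.** Assumed inputs: 60 treated, a pool of 600, four covariates, 1,500 runs per scenario. The Monte Carlo error at a size of 0.05 is √(0.05 × 0.95/1,500) ≈ 0.006. With full sets, strongly prognostic covariates and no case-mix shift, the sizes were:
- chi-squared 0.026
- set-level t-test 0.028
- Mantel-Haenszel by set 0.029
- covariate-adjusted 0.046

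Another run of this scenario gave power of 78% for chi-squared and 84% for the adjusted, set-clustered estimate. The gap was 2 to 3 points with weakly prognostic covariates. Because the set-based tests were as conservative as chi-squared here, covariate adjustment is what recovers the power in this scenario. When case-mix shift was added, set-based tests did restore the size (about 0.045 v 0.02).

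A further simulation with a pool of 500 gave chi-squared sizes of about 0.03 to 0.055. Power was below that of the adjusted, weighted, set-clustered risk difference in every scenario: by 1 to 6 points with little shift and 6 to 16 with marked shift.

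**5. Shift in the estimate.** Suppose there is no true effect and 20 sets each have 1, 2 and 3 controls.
- Risk 0.45 in all sets: no bias, size 0.05.
- Risks 0.35, 0.45, 0.55 by set size: pooled control rate (20 × 0.35 + 40 × 0.45 + 60 × 0.55)/120 = 58/120 = 48.3%, against 45% in treated patients. Bias −3.3 points, size 0.065.
- Risks 0.25, 0.45, 0.65: 62/120 = 51.7%. Bias about −6.7 points, size 0.12.

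Reversing the risk order reverses the sign. These are deliberately harsh cases. Under simulated matching:
- 0.2 SD caliper, shifts of 0.2 to 0.5 SD per covariate (176 down to about 158 controls): bias at most 0.6 points.
- 0.2 SD caliper, marked shift (mean 148 controls): +1.7 to +2.5 points pooled, 0.0 to 0.2 with sets weighted equally.
- Pool of 500, marked shift: 2 to 3 points pooled, about 1 point or less after adjustment.

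**The case against.** The strongest reply is that the defect is under-specification rather than a wrong test. A reader might infer that the plan prescribes chi-squared for the primary outcome. It does not: 7.1 is a general rule and 7.2 is silent. The trial is also sized and monitored as a one-sample design, so it is not certain that a two-sample p-value decides it. That stands as a limit on the wording. Even so, 7.1 introduces its tests directly after the comparison with historical controls, applies its alpha to all analyses, and has no competitor in the document.

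A reader might also infer that the plan provides for unequal sets. It does not: the ratio is 3:1 throughout, and 180 is 3 × 60, a ceiling that falls if fewer than 60 enrol. The pool looks ample: 1071/30 ≈ 36 patients a month from 1 July 2021, or roughly 500 if the window ran about 14 months (an assumption suggested by a reference accessed in September 2022). Matching without a caliper would fill every set. That stands, so incomplete sets are possible but not planned. Filling every set without a caliper can, however, leave poor matches, which the default test does not adjust for.

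Finally, with ρ at or below 0.10 the size is 0.039 to 0.047 and the power difference is about 2 points or less, which is small.

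**Conclusion.** The point holds as a gap with modest consequences. The only analysis available for the primary comparison is an unadjusted pooled test. With full 3:1 sets and prognostic covariates its size is roughly 0.02 to 0.05, and it loses some power, mainly because it does not adjust for covariates. The pooled difference can shift by about 2 to 3 points under an assumed marked case-mix shift and by less than 1 point with little shift, against a planned difference of 20 points.

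Three stronger readings are not supported. With full sets, pooling does not inflate false positives; the error runs the other way. Unequal set sizes alone do not cause bias; set size must also be related to outcome risk. And respecting the sets does not by itself recover the lost power when there is no case-mix shift.

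The figures rest on assumed within-set correlation, covariate strength, case-mix shift, pool size and a two-sided alpha. The documents give none of these directly.

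**What to change.** In 7.2, state that the primary estimate is a risk difference, with confidence interval, from a regression on the matched sample. It should be adjusted for the propensity-model covariates, with each control weighted by 1/(number of controls in its set) and standard errors clustered on matched set. If every set is full the weight is 1/3 throughout, so the rule works whether or not shortfalls occur.

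Use the same approach for the EHR-derived secondary outcomes compared with controls, and keep the 7.1 tests for descriptive tables. Conditional logistic regression should not be listed as an alternative, because it estimates a different quantity (a conditional odds ratio).

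The cost is one paragraph of text, slightly more analysis work and reliance on a regression model. No new data are needed.
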